**Table 8 - PFS analysis - Event and censoring rules**

[figure not shown]
Situation	Date of outcome	Outcome	Category
No baseline tumor assessments	Date of first dose	Censored	No baseline tumor assessments
No evaluable post-baseline tumor assessments	Date of first dose	Censored	No evaluable post-baseline tumor assessments
Ongoing and no documented progression	Date of the last evaluable tumor assessment documenting no progression	Censored	Ongoing without progression
Documented progression (or Death) at or between scheduled visits	Date of progression (or Date of death)	Event	Documented progression (or Death without documented progression)
Documented progression (or Death) occurring after two or more non-evaluable tumor assessment a	Date of the last evaluable tumor assessment documenting no progression	Censored	Event occurred after two or more missed tumor assessment
Initiation of further anti-cancer therapy	Date of the last evaluable tumor assessment before start date of further anti-cancer therapy	Censored	Initiation of further anti-cancer therapy

a An event occurring at least 19 weeks (excluded) after the last evaluable tumor assessment

Time to response (TTR) is defined as the time interval from the administration of the first IMP dose to the first documented CR or PR which is confirmed by a subsequent response. The TTR will be summarized descriptively.

Clinical Benefit Rate (CBR) is defined as the proportion of participants who achieved confirmed CR or PR at any time or SD for at least 6 months. The CBR and corresponding 90% Clopper Pearson 2-sided CI will be derived.

## 4.6 MULTIPLICITY ISSUES

There is no formal statistical test performed. Therefore, no multiplicity issue applies.

## 4.7 OTHER SAFETY ANALYSES

All safety analyses will be performed on the safety population as defined in [Section 3](#), unless otherwise specified, using the following common rules:

- The analysis of the safety variables will be essentially descriptive, and no testing is planned.

### 4.7.1 Extent of exposure

#### 4.7.1.1 *Overall exposure*

The dose information will be assessed by the following variables:

- Overall number of cycles started, defined by the number of cycles in which at least one dose of any study interventions is administered.
- Duration of IMP exposure (in weeks) is defined as (Last day of exposure – first day of exposure +1)/7.
- The first day of exposure is defined as the first administration date with non-zero dose for at least one of the IMP.

The last day of exposure is the day before the theoretical date of the next administration (after the last administration), defined as the maximum between:

- The last administration date + 3 for SAR442720

The last administration date + 20 for Pembrolizumab given at 200 mg IV Q3W or + 41 for Pembrolizumab given at 400 mg IV Q6W

The total number of cycles started will be summarized as a quantitative variable and by category (1-3 cycles, 4-6 cycle, ..... ,  $\geq$ 16 cycles). The duration of overall exposure will be summarized quantitatively.

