 - Investigator believes that it is in the best interest of the participant to withdraw from the study
- Pregnancy
- Lost to follow-up
- Sponsor's decision to terminate the study

Participants who have stable disease as best response will be allowed to continue on treatment provided the investigator believes it is in the participant's best interest and none of the above criteria have been met.

During the conduct of the study, in cases where premature discontinuation of SAR442720 is required, the participant may continue pembrolizumab or adagrasib treatment, upon Investigator decision and in agreement with the Study Medical Manager. Likewise, in cases where premature discontinuation of pembrolizumab or adagrasib is required, the participant may continue SAR442720 treatment if there is presence of, or potential for, clinical benefit as assessed by the Investigator and Study Medical Manager.

Participants who discontinue study treatment should complete the safety follow up or EOT visit, within 30 days after the last treatment dose. Participants who do not withdraw consent will also undergo long term follow up until death or end of study or lost to follow-up.

Refer to SoA for data to be collected at the time of intervention discontinuation and follow-up and for any further evaluations that need to be completed.

Handling of participants after definitive intervention discontinuation

Participants will be followed-up according to the study procedures specified in this protocol up to the scheduled date of study completion, or up to recovery or stabilization of any AE to be followed-up as specified in this protocol, whichever comes last.

If possible, and after the definitive discontinuation of intervention, the participants will be assessed using the procedure normally planned for the last dosing day with the IMP including a PK sample, if appropriate.

All cases of definitive intervention discontinuation must be recorded by the Investigator in the appropriate pages of the eCRF when considered as confirmed.

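### SAP 4.7.1.1 leaves adagrasib out of the end date for overall exposure, so Part-3 duration is understated when adagrasib outlasts SAR442720, and no adagrasib dose-exposure summary is planned

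*SAP*

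**What the plan says.** SAP 4.7.1.1 gives the duration formula: "Duration of IMP exposure (in weeks) is defined as (Last day of exposure – first day of exposure +1)/7". The first day is "the first administration date with non-zero dose for at least one of the IMP". For the end date it says: "The last day of exposure is the day before the theoretical date of the next administration (after the last administration), defined as the maximum between". Two entries follow. One is "The last administration date + 3 for SAR442720". The other is "The last administration date + 20 for Pembrolizumab given at 200 mg IV Q3W", with + 41 for the 400 mg six-weekly schedule. The same section counts overall cycles started as "the number of cycles in which at least one dose of any study interventions is administered".

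Drug-specific exposure is set out for SAR442720 (4.7.1.2) and pembrolizumab (4.7.1.3). The next section is 4.7.2, Laboratory variables. SAP Table 3 (safety population) names adagrasib as an IMP.

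On what happens when SAR442720 has to be stopped early, Protocol 7.1.1 says "the participant may continue pembrolizumab or adagrasib treatment, upon Investigator decision and in agreement with the Study Medical Manager". The ocular entries of Protocol Appendix 9, Table 27 likewise describe Part-3 situations in which SAR442720 is stopped for good and adagrasib may go on.

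**The concern.** The start of exposure and the cycle count use every IMP, but the end of exposure uses only two of the three. In Part-3 one of those two, pembrolizumab, is never given, so the maximum reduces to the SAR442720 term. A participant who stops SAR442720 and stays on adagrasib keeps adding cycles while the reported duration stands still, and the two figures would disagree within one exposure summary.

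The missing subsection matters separately. In Part-3A, DL2 to DL3a (SAR442720 140 mg at both) and DL3b to DL4 (200 mg at both) differ only in adagrasib, 400 against 600 mg BID (Protocol Table 14). A reader comparing those levels needs to know how much adagrasib was actually received. The SAP plans no summary of its number of doses, duration, cumulative dose, actual, planned or relative dose intensity, or dose modifications. SAP Table 5 lists TEAEs leading to dose modification by drug for SAR442720 only.

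**Working it through.** The documents state no figure that depends on this rule, so there is none to reproduce. The check applies the SAP formula to assumed Part-3 histories.

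**Inputs from the documents**
- Duration = (last day − first day + 1)/7 weeks (SAP 4.7.1.1).
- Last day in Part-3 = last SAR442720 date + 3, because no pembrolizumab is given (SAP 4.7.1.1).
- SAR442720 on Day 1 and Day 2 of each week, adagrasib twice daily, 21-day cycles (Protocol 4.1, Part-3A; Table 4).

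**Assumptions**
- The stopping days are illustrative. The documents give no frequency for SAR442720 stopping alone.
- Day 1 is the first dose of both drugs.
- For adagrasib the last day of exposure is the last administration date, + 0 days.

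**Formulas with first day = 1**
- SAP rule: (last SAR442720 day + 3)/7.
- With adagrasib in the maximum: max(last SAR442720 day + 3, last adagrasib day)/7.

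| History | Last SAR442720 day | Last adagrasib day | SAP rule (weeks) | With adagrasib (weeks) | Shortfall (weeks) |
|---|---|---|---|---|---|
| Both stop at end of Cycle 6 | 121 | 126 | 124/7 = 17.71 | 126/7 = 18.0 | 0.29 |
| SAR442720 stops at end of Cycle 4 | 79 | 126 | 82/7 = 11.71 | 18.0 | 6.29 |
| SAR442720 stops at end of Cycle 2 | 37 | 126 | 40/7 = 5.71 | 18.0 | 12.29 |
| SAR442720 stops at end of Cycle 1 | 16 | 126 | 19/7 = 2.71 | 18.0 | 15.29 |
| SAR442720 stops at end of Cycle 2, longer adagrasib | 37 | 168 | 40/7 = 5.71 | 168/7 = 24.0 | 18.29 |

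In the last row the shortfall is 18.29/24 = 76% of the true duration. In the fourth row adagrasib is taken through day 126 = 6 × 21, so the participant has six cycles started beside 2.71 weeks of overall exposure.

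**Is the omission a redaction, an extraction loss or deliberate scoping?** The SAP table of contents lists 4.7.1.1 to 4.7.1.3 and then 4.7.2, and the body matches, so no subsection has dropped out. The SAP covers Parts 3A and 3B in 1.1 and 1.2, tabulates TEAEs leading to permanent discontinuation of adagrasib (Table 5), and declares no changes from the protocol-planned analyses (5.2). The exposure section was simply not extended to the third drug.

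**The case against.** The strongest reply is that little depends on this. The safety analyses are descriptive with no testing (SAP 4.7), and no primary or secondary endpoint uses exposure duration. When both drugs stop together the error is two days. A large error needs SAR442720 to stop alone, which is permitted but whose frequency is unknown. All of that stands, and it limits the size of the point.

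The sponsor could also say that the general principle in the end-date sentence, the day before the next dose would have been due, already covers adagrasib. But that sentence goes on to define the date by an explicit list, and a programmer will code the list. The principle does not supply the missing subsection either.

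Three stronger readings are tempting, and the documents do not support them:

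- **Adagrasib exposure goes wholly unreported.** It counts in cycles started and in the first day of exposure. Its concentrations, and its Part-3A PK parameters, are summarised (SAP 4.8.1). SAEs related to it and TEAEs leading to its permanent discontinuation are tabulated (Table 5). What is missing is the summary of dose received, duration and dose modification.
- **The DLT assessment or MTD is compromised.** The criterion of delivering at least 66.7% of adagrasib (Protocol 4.1.1) and the 28 of 42 doses for DLT-evaluability (SAP Table 3) are Cycle 1 determinations for each participant. Neither uses these summaries.
- **AE rates are distorted by a mismatched window.** The on-treatment period runs to the last IMP administration + 30 days (SAP 4.1), so it is longer than exposure by design. The SAP plans numbers and percentages of participants, not exposure-adjusted rates.

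**Conclusion.** The rule is wrong as written for Part-3: overall exposure ends at the last SAR442720 dose + 3 days whatever happens with adagrasib. The understatement ranges from about 0.3 weeks (both drugs stopping together at a cycle end) to between 6 and 18 weeks in the histories where adagrasib continues alone. Those histories are assumed, and the effect on the Part-3 summary depends on how many participants follow such a course, which the documents do not say. Separately, the SAP plans no summary of adagrasib dose received, in a part where two escalation steps change adagrasib only. The consequences stop at the exposure reporting and any informal reading of Part-3 safety against it. ORR, DLT counts, the MTD recommendation and the planned AE percentages are unchanged. It should be corrected before the Part-3 exposure tables are programmed.

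**What to change.** 1. In SAP 4.7.1.1, add a third term to the maximum for Part-3: the last administration date for adagrasib, + 0 days. State the + 0 as the convention for a twice-daily drug, so that a last day with only the morning dose taken is handled in the same way.
2. Add a subsection 4.7.1.4, Adagrasib exposure, covering number of doses, cycles started, duration, cumulative dose, ADI, PDI, RDI and dose modifications, by dose level in Part-3A and overall in Part-3B.
3. Do not carry over the omission definition from 4.7.1.2 and 4.7.1.3, which rests on a dose not being given at a scheduled visit. Define adagrasib reductions and omissions for twice-daily home dosing, from the recorded doses and dates.

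The cost is SAP wording and one further set of exposure tables. Protocol 6.4 already requires a record of adagrasib tablets dispensed and taken, and eCRF entry of start and stop dates, delays and reductions. No new data collection or design change is needed.

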#### 4.7.1.2 SAR442720 exposure

The dose information will be assessed by the following:

- Number of doses
- Number of cycles started per participant
- Duration of SAR442720 exposure (in weeks) is defined by (date of last administration of SAR442720 + 3 – date of first administration of SAR442720 + 1)/7
- Actual dose (mg)
- Cumulative dose (mg): the cumulative dose is the sum of all actual doses of SAR442720, given from first to last administration
- Actual dose intensity (ADI in mg/week): defined as the cumulative dose divided by the duration of SAR442720 exposure (in weeks)
- Planned dose intensity (PDI in mg/week): corresponds to the planned dose multiplied by the theoretical total number of doses started and divided by the theoretical cycle duration expressed in weeks (ie, 3weeks per cycle started)
- Relative dose intensity (RDI, in %):  $100 \times \frac{\text{ADI (mg/week)}}{\text{PDI (mg/week)}}$

The total number of doses, number of cycles started by participant will be summarized as a quantitative variable and by category (1-3 cycles, 4-6 cycle, ..... ,  $\geq 16$  cycles). Duration of SAR442720 exposure, cumulative dose, ADI and RDI will be summarized quantitatively.

The following variables will be derived to describe dose modifications:

- Dose reduction: The first administration will not be counted as a dose reduction. For the second and subsequent SAR442720 administrations, dose reduction will be determined by comparing the current dose level to the previous dose level. If the current dose level is below the dose level interval of the previous dose administration, then the current dose level is considered reduced.
- Dose omission is defined as a dose not administered at the scheduled visit but administered afterwards. “Not taken” information from eCRF dosing page to be taken into account to identify dose omissions.
- Dose delay: a dose is deemed to have been delayed if the dose is administrated up to 3 days after the theoretical date

Dose modifications will be analyzed by participant, cycle and dose as follows:

- **Participant** (number of participants treated will be used as denominator)
  - Number (%) of participants with at least 1 dose reduction
  - Number (%) of participants with at least 1 dose omission

- **Cycle** (number of cycles started will be used as denominator)
  - Number (%) of cycles with at least 1 dose reduction
  - Number (%) of cycles with at least 1 dose omission

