#### Part-2

The expansion cohort (Part-2), un-controlled, non-randomized, open-label study will assess the antitumor activity and safety of SAR442720 combined with pembrolizumab in participants with lung cancer.

Part-2 will assess the antitumor efficacy and safety of adding SAR442720 to therapeutic approaches with documented efficacy profile as 1L NSCLC therapy.

- Cohort A1: participants with PD-L1 TPS  $\geq 50\%$  NSCLC to receive SAR442720 + pembrolizumab as 1L therapy.
- Cohort A2: participants with PD-L1 TPS 1%-49% NSCLC to receive SAR442720 + pembrolizumab as 1L therapy.

Part-2 of the study will start at the RP2D for SAR442720 defined in Part-1. The SAR442720 RP2D will be 200 mg BIW, such Day 1 and Day 2 of each week, administered orally (21 days per cycle). Pembrolizumab will be administrated as a dose of 200 mg using 30 minutes IV infusion on Day 1 every 3 weeks (21 days cycle) or a dose of 400 mg using 30 minutes IV infusion on Day 1 every 6 weeks (42 days cycle).

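### The fixed 3-day tail on SAR442720 exposure fits Day 1/Day 4 dosing but not the Day 1/Day 2 dosing of Parts 2 to 4, so fully compliant participants show a relative dose intensity above 100%

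*SAP*

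**What the plan says.** SAP 4.7.1.1 (Overall exposure) gives the principle: "The last day of exposure is the day before the theoretical date of the next administration". It then turns this into a fixed number of days: "The last administration date + 3 for SAR442720", against +20 or +41 for pembrolizumab depending on whether it is given every 3 or every 6 weeks. SAP 4.7.1.2 (SAR442720 exposure) uses the same fixed offset in the drug-specific duration, "date of last administration of SAR442720 + 3", with no condition on schedule.

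That duration is the denominator of actual dose intensity (ADI), which is cumulative dose per week of exposure. Planned dose intensity (PDI) "corresponds to the planned dose multiplied by the theoretical total number of doses started", divided by the theoretical cycle length, "3weeks per cycle started". RDI is 100 × ADI/PDI.

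On schedule, the protocol synopsis starts Part-1 on Day 1 and Day 4 of each week and allows alternatives, including Day 1 and Day 2. For Part-2 the SAP itself states: "The SAR442720 RP2D will be 200 mg BIW, such Day 1 and Day 2 of each week". The protocol synopsis gives Day 1/Day 2 for Part-4 as well, and every dose level in protocol Table 14 (Part-3A) is Day 1/Day 2.

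**The concern.** An offset of 3 days is the gap that follows a Day 4 dose. It looks as if it was set for the Part-1 starting schedule and not adapted when Day 1/Day 2 dosing became the rule in the later parts. The pembrolizumab offsets were set separately for its two schedules; the SAR442720 offset was not.

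Numerator and denominator of RDI then cover different lengths of time. ADI divides by a shortened period, PDI by whole cycles. A participant who takes every dose should score 100%, and a reader cannot interpret a value above that. The distortion is largest for short exposures. It also differs by schedule, so if both schedules were used in Part-1, equal compliance could appear as different RDI values.

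**Working it through.** **Inputs.** 21-day cycle and 6 planned SAR442720 doses per cycle (protocol 4.1.2; SAP Table 3). Duration in weeks = (last dose day + 3 − first dose day + 1)/7 (SAP 4.7.1.2). ADI, PDI and RDI as defined there, with PDI taken at 6 doses per cycle started. The illustration uses 200 mg; the dose cancels in RDI.

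**Step 1: the plan's own +3 on Day 1/Day 4.** Doses fall on days 1, 4, 8, 11, 15 and 18, and the next is due on day 22. The day before is day 21 = 18 + 3. Duration = 21/7 = 3 weeks, ADI = 1200/3 = 400 mg/week, PDI = 1200/3 = 400 mg/week, RDI = 100%. The plan's offset reproduces. The pembrolizumab offsets also do: 21/7 = 3.0 weeks and 42/7 = 6.0 weeks.

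**Step 2: the same formula on Day 1/Day 2.** Doses fall on days 1, 2, 8, 9, 15 and 16, and the next is due on day 22. The day before is day 21 = 16 + 5, but the formula stops at 16 + 3 = day 19. Duration = 19/7 = 2.714 weeks, ADI = 1200/2.714 = 442.1 mg/week, PDI = 400 mg/week, RDI = 110.5%.

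**Step 3: general form.** After c complete, fully compliant Day 1/Day 2 cycles the duration is 21c − 2 days, so RDI = 100 × 21c/(21c − 2).

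| Complete cycles | SAP formula | With +5 |
|---|---|---|
| 1 | 21/19 = 110.5% | 100% |
| 2 | 42/40 = 105.0% | 100% |
| 4 | 84/82 = 102.4% | 100% |
| 6 | 126/124 = 101.6% | 100% |
| 8 | 168/166 = 101.2% | 100% |

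**Step 4: one missed dose that is not the last.** After 1 cycle, 5/6 × 21/19 = 92.1% instead of 83.3%. After 2 cycles, 11/12 × 42/40 = 96.2% instead of 91.7%.

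**Step 5: last dose taken on a Day 1.** Suppose only the final dose of Cycle 1 is missed, so the last dose is on day 15 (5 doses, 1000 mg).

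- SAP formula (+3): 18 days, ADI 388.9 mg/week, RDI 97.2%.
- Literal day before the next dose (+0): 15 days, ADI 466.7 mg/week, RDI 116.7%.
- Close of the dosing week (+6): 21 days, ADI 333.3 mg/week, RDI 83.3%, which equals 5/6.

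So applying the SAP's principle literally would not cure the problem; closing the dosing week does.

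**Step 6: overall exposure (SAP 4.7.1.1).** This takes the later of the SAR442720 and pembrolizumab end dates. In a Q3W cycle, pembrolizumab on day 1 gives day 21, later than day 19, so the SAR442720 error does not show. For Part-3 the SAP lists no adagrasib term, so the SAR442720 offset alone sets the end date.

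**The case against.** The best defence is that little depends on this. RDI is not an endpoint in any part, SAP 4.7 calls the safety analyses essentially descriptive, and the error is a fixed 2 days that fades with time. The protocol synopsis expects a median of 6 months on treatment in Parts 1 and 4, roughly 8 to 9 cycles, where RDI is overstated by about 1 percentage point. The 110.5% figure belongs to someone who completes exactly one cycle. In Parts 2 and 4, overall exposure is usually set by the pembrolizumab offset. All of this stands and limits the weight of the point.

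Two stronger readings are tempting and should not be drawn.

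- A reader might infer that every SAR442720 duration, ADI and RDI in Parts 2 to 4 is wrong and that RDI is always too high against the SAP's own rule. That does not follow. After a Day 1 dose the next is due the following day, so +3 is longer than the rule gives, and RDI falls below 100% (97.2% in step 5; 99.7% if this happens in week 24).
- A reader might infer that missed doses are hidden and tolerability overstated. The SAP separately reports number of doses, cumulative dose, and participants and cycles with a reduction or omission, using the eCRF record of doses not taken. Tolerability is judged from adverse events, discontinuations, dose modifications and DLTs, and DLT evaluability counts doses taken. None of these uses the SAP's RDI.

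A further objection is that PDI is itself unclear. If the number of doses started means doses actually taken, a participant who completes only 2 weeks of one cycle has PDI = 800/3 = 266.7 mg/week and RDI = 400/266.7 = 150%, even on Day 1/Day 4. That is a separate ambiguity. For complete, fully compliant cycles both readings give the figures in step 3, so it does not remove the point, but the text should settle it.

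**Conclusion.** The point holds as an internal inconsistency that produces a wrong reported number. The +3 offset meets the SAP's own definition only after a Day 4 dose on Day 1/Day 4. On Day 1/Day 2, after a Day 2 dose, exposure ends 2 days early and full compliance gives an RDI above 100%: by 10.5 percentage points at 1 cycle, 5.0 at 2, 2.4 at 4 and about 1.2 at 8.

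The reach is the descriptive SAR442720 duration, ADI and RDI in Parts 2 to 4, any Part-1 participants dosed on Day 1/Day 2, and overall exposure in Part-3. No efficacy result, DLT classification or dose decision depends on it.

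The figures assume doses on their nominal days, 21-day cycles without delay, a Day 2 dose as the last one taken (except step 5), and PDI at 6 planned doses per cycle started. The point concerns the analysis formula only and takes no position on the dosing schedule. It should be corrected before the exposure tables are produced.

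**What to change.** In SAP 4.7.1.1 and 4.7.1.2, replace the fixed +3 by the close of the last dosing week: last dose +6 after a Day 1 dose, +5 after a Day 2 dose, +3 after a Day 4 dose. Reword the definition in 4.7.1.1 for SAR442720 to match, because the day before the next dose would give +0 after a Day 1 dose. The new rule gives 100% for complete cycles at full compliance on either schedule, and 83.3% when only the final dose of a single cycle is missed.

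State that PDI uses 6 planned doses per cycle started. Present Part-1 SAR442720 exposure by schedule if both schedules were used.

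The cost is minor wording and programming, with no new data and no change to design. Since the new offsets are never shorter than 3 days, reported RDI stays the same or becomes slightly lower for most participants, with larger drops only for very short exposures.
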